#### 6.5.2.3 AEs by Preferred Term

The following summary tables of unsolicited AEs will be provided by PT sorting by frequency on the mRNA-1083 group:

All unsolicited AEs, SMQ

# 6.5.2.4 AEs by Severity

The following summary tables of AEs will be provided by SOC, PT and the maximum severity or toxicity Grade using frequency counts and percentages by treatment arm (as defined in Section 6.1):

All unsolicited AEs,

All unsolicited AEs that are treatment-related.

# 6.5.2.5 Independent Cardiac Event Adjudication Committee

An independent CEAC comprised of medically qualified personnel, including cardiologists, will review suspected cases of myocarditis, pericarditis, and myopericarditis to determine if they meet CDC criteria for "probable" or "confirmed" events. The CEAC members will be blinded to study treatment. Details regarding the CEAC composition, responsibilities, procedures, and frequency of data review can be found in the CEAC charter.

A summary table will be provided based on the data adjudicated by the CEAC, as the primary analysis of cardiac events.

#### 6.5.2.6 Subgroup Analysis

Analysis of unsolicited AEs will be conducted for subgroups as defined in Table 4 of Section 6.1 for the following summaries:

Overall summary of the unsolicited AEs,

All unsolicited AEs up to 28 Days After Injection,

All unsolicited AEs up to 28 Days After Injection that are treatment-related,

All unsolicited AEs up to 28 Days After Injection by severity,

All serious unsolicited AEs up to 28 Days After Injection and Throughout the Study,

All serious unsolicited AEs that are treatment-related up to 28 Days After Injection and Throughout the Study.

#### 6.5.2.7 Death

Total number of deaths due to any cause and time of death from injection (numeric and by time point window) may be summarized in a table. In addition, number of participants with occurrences of unsolicited AE leading to death will be summarized by SOC and PT using frequency counts and percentages. A listing of deaths including cause of death, and a listing of unsolicited AEs in participants who died will be provided.

# 6.5.3 Clinical Safety Laboratory Tests

No scheduled laboratory assessments for safety are planned. This is based on the absence of clinically significant abnormal laboratory findings in the Phase 1/2 study mRNA-1083-P101 in adults.

#### 6.5.4 Vital Signs

Vital sign measurements will include systolic and diastolic blood pressure, heart rate, respiratory rate, and body temperature (preferred route is oral). On the day of study injection, vital sign measurements will be collected once before and at least 30 minutes after study injection. Vital signs may be collected at other study visits in conjunction with a symptom-directed physical examination.

Following injection, any abnormal vital sign measurement should be assessed by the Investigator to determine if it meets AE reporting criteria per protocol and reported as an AE in EDC, if appropriate.

The Toxicity Grading Scale for Healthy Adult and Adolescent Volunteers Enrolled in Preventive Vaccine Clinical (DHHS, 2007) available in Appendix G will be used to categorize vital sign measurements observed during this clinical trial.

Observed values and changes from pre-injection (Baseline) to post-injection (at Day 1, 30 minutes after study intervention) for all vital sign measurements will be summarized by treatment arm (as defined in Section 6.1). A toxicity grade shift table of the vital signs from pre-injection to post-injection will be provided as well.

A listing containing individual participant vital sign measurement data will be provided. Additionally, participant with any abnormal post-baseline vital sign measurement where toxicity grade (Grade 3 or higher) will be listed separately: if a participant has a vital sign result with Grade 3 or higher abnormality after injection visit, then all results for that participant will be presented in the listing.

If multiple values are collected within a post-baseline visit/timepoint, the last assessment will be used in the by-visit summary tables. Unscheduled visits (including early termination) will not be summarized in by-visit summaries of data but may contribute to either baseline or post-baseline worst-case (maximum, minimum, etc.) values when applicable.

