8.3.2. Vital Signs

Vital sign measurements will include systolic and diastolic blood pressure, heart rate, respiratory rate, and body temperature (preferred route is oral). The participant will be seated for at least 5 minutes before all measurements are taken. Vital signs will be measured at the timepoints indicated in the SoA in Section 1.3. On the day of study injection, vital sign measurements will be collected once before and at least 30 minutes after study injection. Vital signs may be collected at other study visits in conjunction with a symptom-directed physical examination.

Following study injection, any abnormal vital sign measurement should be assessed by the Investigator to determine if it meets AE reporting criteria per protocol and reported as an AE in EDC, if appropriate. The Investigator will continue to monitor the participant with additional assessments until the vital sign value has reached the reference range, returns to the vital sign value at Baseline, is considered stable, or until the Investigator determines that follow-up is no longer medically necessary.

Participants who are febrile (body temperature ≥38.0°C/100.4°F) before injection on Day 1 should be rescheduled within the relevant window period to receive the study injection. Criteria for delay of study injection are provided in Section 6.7. If fever is clinically concerning, participant should not be dosed. Participants who are afebrile with minor illnesses may receive the study injection at the discretion of the Investigator.

When procedures overlap and are scheduled to occur at the same timepoint, the order of procedures should be vital sign measurements and then blood collection.

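### The last-assessment rule in SAP 6.5.4 can let a recovered reading replace a transient post-injection vital-sign abnormality in the by-visit summaries, if repeats are recorded under the same timepoint

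*SAP*

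**What the plan says.** SAP 6.5.4 plans a summary by treatment arm of observed vital signs and of their change from the pre-injection to the Day 1 post-injection reading. Where a timepoint holds more than one value, the rule is: "If multiple values are collected within a post-baseline visit/timepoint, the last assessment will be used in the by-visit summary tables". The same section adds: "A toxicity grade shift table of the vital signs from pre-injection to post-injection will be provided as well". It does not say whether the post-injection grade in that table is the first, last or worst.

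On unscheduled visits, SAP 6.5.4 says: "Unscheduled visits (including early termination) will not be summarized in by-visit summaries of data", and continues: "but may contribute to either baseline or post-baseline worst-case (maximum, minimum, etc.) values when applicable". No worst-case vital-sign table is named. All vital-sign data are listed, and participants with a Grade 3 or higher value after injection are listed separately with all their results.

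Protocol 8.3.2 sets the measurement schedule: "On the day of study injection, vital sign measurements will be collected once before and at least 30 minutes after study injection". After an abnormal post-injection value: "The Investigator will continue to monitor the participant with additional assessments until the vital sign value has reached the reference range". The sentence then gives the other stopping conditions: "returns to the vital sign value at Baseline, is considered stable, or until the Investigator determines that follow-up is no longer medically necessary". The Investigator also judges whether each abnormal value should be reported as an adverse event.

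**The concern.** These summaries are there to show acute change shortly after injection. A rule that keeps the last of several values answers a different question, namely how participants were once follow-up had ended. Repeats are triggered by abnormal values, so the choice of value depends on the outcome: a participant with a normal first reading keeps it, while a participant with an abnormal one may have it replaced.

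Two things are at stake. Acute changes may be under-reported in the tables, and a difference between arms may shrink, because the arm with more abnormal readings has more of them open to replacement. No safety laboratory tests are scheduled (Protocol 8.3.3), so these readings are a main source of clinic-measured acute safety data.

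**Working it through.** The documents give no rate of vital-sign abnormality, so there is no stated figure to reproduce. The check sets the passages side by side.

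1. **Can several values share the post-injection timepoint?** Yes. Protocol 8.3.2 gives the post-injection reading a lower time bound (30 minutes) and no upper one, so a repeat taken later in the same clinic visit can fall under it.
2. **Why would repeats exist?** Only one post-injection reading is scheduled. The vital-signs section asks for more when that reading is abnormal, so most repeats follow an abnormal value.
3. **What is the last value likely to be?** Of the four stopping conditions, two are recovery (in range, or back at Baseline). The other two (stable, or an Investigator decision) can leave the last value abnormal. The last value is therefore often, but not always, a recovered one.
4. **Which tables does the rule reach?** Its wording covers by-visit summary tables, which include observed values and change. The shift table is described in a separate sentence with no selection rule. The last-assessment rule is the only within-timepoint rule in SAP 6.5.4, so a programmer might apply it there, but the text does not say so.
5. **What if the repeat is recorded as an unscheduled visit?** It is then left out of the by-visit summaries and the first value stands. The documents do not say how sites record same-day repeats.
6. **Does the abnormal value survive elsewhere?** It does in the full listing, and in the separate listing if Grade 3 or higher. It enters the adverse event tables if the Investigator reports it. SAP 6.1 lets unscheduled measurements feed maximum and minimum values for safety analyses, but no such vital-sign table is specified.

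**Example (illustrative values, graded with SAP Table 8).** Systolic pressure is 128 before injection, 149 at the post-injection reading (Grade 1) and 134 on a repeat (ungraded).

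- First value: change = 149 - 128 = +21 mm Hg, shift from no grade to Grade 1.
- Last value: change = 134 - 128 = +6 mm Hg, and no shift if the same rule is used for grading.

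The 149 is below Grade 3, so it is not in the separate listing. Unless it is reported as an adverse event, no arm-level table shows it.

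**Range under assumptions.** Let x be the share of an arm with a post-injection abnormality, and r the share of those re-measured in the same timepoint and recovered. A last-value table shows x(1 - r) and misses xr. Neither x nor r is in the documents. For 2000 per arm:

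- x = 2%, r = 25%: 2000 × 0.02 × 0.25 = 10 of 40 participants missed.
- x = 10%, r = 75%: 2000 × 0.10 × 0.75 = 150 of 200 participants missed.
- r = 0 (no repeat shares the timepoint): none missed.

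If r is the same in both arms, the arm difference becomes (1 - r) times its true size, which is 75% to 25% of it over this range.

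**The case against.** The strongest case on the other side is that nothing may be displaced. One post-injection reading is scheduled, and if follow-up readings are recorded as unscheduled, SAP 6.5.4 excludes them and the first value stands. That is correct, and it makes the concern conditional. It does not remove it, because the SAP leaves the outcome to site recording practice.

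Three stronger readings are tempting and are not supported.

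- A reader might infer that abnormal values are re-measured until normal. The protocol also allows stopping when the value is stable or follow-up is judged unnecessary.
- A reader might take the shift table to be built on last values. The SAP does not say which value it grades.
- A reader might treat the shift table as the only arm-level view of acute change. It is not. SAP 6.5.4 also tabulates observed values and changes. Fever is a solicited reaction, entered in the eDiary as the highest reading of the day (Protocol 8.3.7) and summarised by arm and grade (SAP 6.5.1.2). Abnormal values reported as adverse events enter the tables in SAP 6.5.2.

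Measurement noise also matters. A reading just over a cut-off is partly error, so some values that fall on repeat were never real acute changes. A modelled percentage of events lost would count that noise as lost signal, so none is claimed here. For the same reason, replacing the last value by the worst value throughout would not be neutral: several post-injection readings set against one pre-injection reading inflate apparent worsening.

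**Conclusion.** The point holds in a conditional form. SAP 6.5.4 contains a rule that, combined with the follow-up in Protocol 8.3.2, can select post-injection values by outcome. The by-visit summaries are affected if repeats are recorded under the Day 1 post-injection timepoint. The shift table is affected only if the same rule is used for it, which is unspecified. The real gap is transient Grade 1-2 change in blood pressure, heart rate or respiratory rate, which could be absent from every arm-level table unless reported as an adverse event.

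The documents do not allow the effect to be sized. The 10 to 150 participants per arm above rest wholly on assumed rates, and the effect is zero if repeats are recorded as unscheduled. Severity is minor: vital signs are descriptive, are not among the listed safety endpoints, and support no tested hypothesis.

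**What to change.** In SAP 6.5.4:

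- For the Day 1 post-injection timepoint, replace the last-assessment rule with the first scheduled post-injection value, for both observed values and change from baseline.
- State that the shift table uses that same first scheduled value.
- Add a row or supplementary table giving the highest post-injection grade including repeats. Label it worst-case, with a note that comparing several post-injection readings with one pre-injection reading inflates worsening in both arms.
- State that same-day repeats never replace the scheduled value, however sites record them.

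The cost is a few sentences of SAP text and a little programming, with no new data. Reported rates of abnormal values may look slightly less favourable.

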#### 6.5.5 Pregnancy Testing

For participants of childbearing potential, a point-of-care urine pregnancy test will be performed at the Screening Visit and before injection. At the discretion of the Investigator, a pregnancy test either via blood or point-of-care urine can be performed at any time. For participants assigned female at birth and of nonchildbearing potential, the FSH level may be measured at the Screening Visit, as necessary, and at the discretion of the Investigator, to confirm menopausal status.

A listing containing individual participant pregnancy test results will be provided for the pregnancy tests and FSH blood levels.

# 6.5.6 Other Safety Data

#### 6.5.6.1 Safety Telephone Calls

A safety telephone call is a telephone call made to the participant by trained site personnel. This call will follow a script, which will facilitate the collection of relevant safety information.

#### 6.5.6.2 Assessment for Respiratory Viral Infection

All participants will provide nasal swab samples before the injection on Day 1 for assessment of infection with respiratory pathogens, including influenza viruses and SARS-CoV-2, as influenza or COVID-19 symptoms may confound reactogenicity assessments.

#### 6.5.6.3 Physical examination

A full physical examination will include, at a minimum, assessments of skin, head, ears, eyes, nose, throat, neck, thyroid, lungs, heart, cardiovascular system, abdomen, lymph nodes, and musculoskeletal system and extremities. Height and weight will also be measured and recorded. At Screening, the body mass index will be calculated using the formula weight (kg) / (height [m])^2.

# 6.6 Other Exploratory Endpoints

#### 6.6.1 Genetics

A prospective research sample, to be used for future genetic research, will be collected from participants who have consented to participate in the genetic analysis component of the study. Participation is optional. Participants who do not wish to participate in the genetic research may still participate in the study. The genetic analyses will not be covered in the plan and will be developed in a separate plan as needed.

#### 6.6.2 Biomarkers

Transcriptomic and genomic samples will be part of the optional biomarker assessment as per the SoA once consented by the study participant. Exploratory assessments may include assessment of biomarkers for safety, reactogenicity, and inflammation. Serologic markers of disease severity, immune response to SARS-CoV-2 or influenza, RT-PCR of nasal swab samples, genetic sequences of SARS-CoV-2 or influenza strains isolated from participants' samples, and genomic and transcriptomic samples may also be evaluated. Samples will be collected according to the schedule described in the SoA in Appendix A and as detailed in the laboratory manual provided separately to sites. The biomarker analyses will not be covered in this SAP and will be developed in a separate analysis plan as needed.

## **6.6.3** Patient Reported Outcomes

All participants will receive eDiary prompts to complete the EQ-5D-5L daily starting at Day 1 (Baseline) through the 7 days after study injection. For Cohort B participants, the WPAI will be collected using the eDiary on Day 1 (Baseline) and Day 8.

A separate analysis plan and report will be developed for analyzing these two endpoints (EQ-5D-5L and WPAI) of patient-reported outcomes.

# 6.7 Planned Analyses

The statistical analyses in this clinical study will be separately planned and performed on the data collected in the 2 substudies Cohorts A and B, respectively, with each substudy independently having its own hypotheses, statistical analyses, and multiplicity control.

Throughout the study, the DSMB will conduct reviews of related SAEs at regular intervals, as outlined by the DSMB charter.

The analysis will be performed by a separate team of unblinded programmers and statisticians. More details can be found in the study data blinding plan.

### 6.7.1 Interim Analysis

The primary analysis of safety and immunogenicity will be performed after all participants of a given substudy have completed the Day 29 visit.

#### **Cohort A Substudy (≥65 Years)**

The primary analysis of safety, reactogenicity, and immunogenicity for Cohort A substudy will occur when all the Cohort A participants have completed the Day 29 visit.

A second interim analysis of Cohort A substudy may be performed after all the Cohort A participants have completed the Day 91 visit.

A combined analysis of Day 29/Day 91 may be performed after all the Cohort A participants have completed the Day 91 visit.

#### **Cohort B Substudy (≥50 to <65 Years)**

The primary analysis of safety, reactogenicity, and immunogenicity for Cohort B substudy will occur when all the Cohort B participants have completed the Day 29 visit.

A second interim analysis of Cohort B substudy may be performed after all the Cohort B participants have completed the Day 91 visit.

A combined analysis of Day 29/Day 91 may be performed after all the Cohort A participants have completed the Day 91 visit.

#### 6.7.2 Final Analysis

Final analysis of all safety, immunogenicity, and efficacy data will be performed once all participants of a given substudy have complete the Day 181 (EoS) visit.

# 7 CHANGES FROM PLANNED ANALYSIS IN PROTOCOL

Not applicable.

# APPENDIX A SCHEDULE OF ACTIVITIES (SOA)

Visit Number	SCRN	1	2	3	4	5	USV
Type of Visit/Contact		C	SC	C	SC	SC/C	C
Month Timepoint				M1	M3	M6	Up to M6
Study Visit		Day 1 (Baseline) a	Day 8	Day 29	Day 91	Day 181 (EoS) b	USV
Window Allowance (Days)	-42	NA	±3	-7 to +3	±5	±14	NA
ICF, demographics, concomitant medications, medical history c	X						
Inclusion/exclusion criteria	X	X					
Physical examination d	X	X		X			
Vital sign measurements e	X	X					
Pregnancy testing f	X	X					
Randomization		X					
Study injection (including 30-minute postdosing observation period) g		X					
Collection of EFS h		X					
Blood collection for humoral immunogenicity i		X j		X		X	
Optional blood collection for future research sample (genomics)		X j					
Optional blood collection for future research sample (transcriptomics)		X j		X			
Nasal swab for virus detection k		X					
Blood collection for SARS-CoV-2 antibodies, nucleocapsid		X j					
eDiary activation for recording solicited ARs		X					

Visit Number	SCRN	1	2	3	4	5	USV
Type of Visit/Contact	C	C	SC	C	SC	SC/C	C
Month Timepoint				M1	М3	M6	Up to M6
Study Visit	SCRN a	Day 1 (Baseline) a	Day 8	Day 29	Day 91	Day 181 (EoS) b	USV
Window Allowance (Days)	-42	NA	±3	-7 to +3	±5	±14	NA
Solicited AR eDiary Reporting 		~30 min postinjection and then daily Day 1 through Day 7					
Review of eDiary for solicited ARs		X	X				
Follow-up safety call m			X		X	X	
eDiary collection of EQ-5D-5L n		Baseline (prei thereafter daily D Day 7 postir	ay 2 through				
eDiary collection of WPAI: General Health V2.0°		X	X				
Recording of unsolicited AEs		X	X	X			
Recording of MAAEs		X	X	X	X	X	
Recording of SAEs p , AESIs, and AEs leading to discontinuation and any concomitant medications relevant to or for the treatment of the events	Хp	X	X	X	X	X	X
Recording of concomitant medications and nonstudy vaccinations q	X	X	X	X	X	X	X
Study completion						X	

Abbreviations: AE=adverse event; AESI=adverse event of special interest; AR=adverse reaction; C=clinic visit; COVID-19=coronavirus disease 2019; D=day; eDiary=electronic diary; EFS=Edmonton Frail Scale; EoS=end of study; EQ-5D-5L=EuroQoL 5-dimension 5-levels; FSH=follicle-stimulating hormone; HRQoL=health-related quality of life; ICF=informed consent form; ILI=Influenza-like Illness; IM=intramuscular; M=month; MAAE=medically attended adverse event; NA=not applicable; SAE=serious adverse event; SARS-CoV-2=severe acute respiratory syndrome coronavirus 2; SC=safety (phone) call; SCRN=Screening; USV=unscheduled visit; WPAI:Viral Resp=Work Productivity and Activity Impairment Questionnaire: Viral Respiratory.

- Screening and Day 1 may be performed on the same day or a different day. Additionally, the Screening Visit may be performed over multiple visits if within the 42-day Screening window.
- b EoS is defined as completion of the last visit of the last participant in the clinical study or last scheduled procedure as shown in the SoA for the last participant in the clinical study globally.
- c Verbal history is acceptable.
- d A full physical examination, including height and weight, will be performed at the Screening Visit; symptom-directed physical examinations may be performed at other clinic visits. Interim physical examinations will be performed at the discretion of the Investigator. Any clinically significant finding identified by a healthcare professional during clinic visits should be reported as an MAAE.
- e Systolic and diastolic blood pressure, heart rate, respiratory rate, and body temperature. The preferred route of temperature assessment is oral. Vital signs will only be collected at Screening and on the day of injection (Day 1), once before and at least 30 minutes after injection. Vital signs will be collected at other clinical visits only in conjunction with a symptom-directed physical examination.
- f A point-of-care urine pregnancy test will be performed at the Screening Visit and before the IM injections on Day 1. At the discretion of the Investigator, a pregnancy test either via blood or point-of-care urine can be performed at any time. The FSH level may be measured at the Screening Visit, as necessary, and at the discretion of the Investigator, to confirm postmenopausal status.
- g All participants will be randomized to receive 2 IM injections, 1 in each deltoid muscle.
- h Assessment of EFS will only be performed for participants aged 65 years and older.
- i Humoral immunogenicity samples on Day 1 and Day 29 will be collected in all participants in Cohort A and Cohort B. Samples for humoral immunogenicity on Day 181 will be collected and analyzed for at least 800 participants of each cohort. These participants will require a clinic visit on Day 181. Plasma and serum from humoral immunogenicity samples will be stored for potential future use.
- j Transcriptomic and genomic samples will be part of the optional biomarker assessment once consented by the study participant. All blood samples must be collected prior to receipt of injection on Day 1.
- k A nasal swab specimen(s) for assessment of pathogens, including influenza virus and SARS-CoV-2, will be collected any time from Day 1 through 6 months after study injection or at EoS if the participants have protocol-defined ILI or symptoms suggestive of COVID-19 or other upper or lower respiratory infection at the Investigator's discretion.
- The eDiary activation and entries will be recorded by the participant at approximately 30 minutes after injection while at the clinic with instruction provided by study staff. Study participants will continue to record in the eDiary each day after they leave the clinic, on the day of injection and for 6 days following injection, for a total of 7 days.
- m Trained study staff will call all participants to collect information related to any AEs, SAEs, MAAEs, AESIs, AEs leading to discontinuation, information on concomitant medications associated with those events, and any nonstudy vaccinations.
- n The EQ-5D-5L consists of the EQ-5D descriptive system and the EQ visual analogue scale (EQ-VAS). All participants will receive eDiary prompts to complete the EQ-5D-5L daily starting at Day 1 (Baseline) through 7 days after study injection. For Day 1 (baseline), participants should complete the EQ-5D-5L questionnaire prior to administration of the study injection.
- o Cohort B only. At baseline, the WPAI questionnaire is to be completed prior to administration of the study injection.
- p SAEs will be collected from the time of informed consent through Day 181 (Month 6) or EoS.
- q All concomitant medications will be recorded through 28 days after injection. Additionally, nonstudy injections and certain concomitant medications will be recorded through Day 181 or EoS.

